### **9.1.2 Documentation and Reporting of Adverse Events**

The observation period for AEs will start with confirmation of signed informed consent at Screening (i.e., at Day -28 to Day -10) and ends at Week 44.

All AEs reported from the time the subject gives written informed consent to participate in the study until 28 days after the last administration of IMP will be recorded, irrespective of whether they were solicited or reported spontaneously by the subject. AE information will be collected and recorded in the eCRF.

For subjects who discontinue early, a Post-Treatment FUV will occur 3 months after the early discontinuation or when another HS therapy has been started, whichever occurs first.

---

Any AEs judged by the investigator to be at least possibly related to treatment with the IMP should be reported to the sponsor regardless of the length of time that has passed since the subject has completed the study.

Every attempt should be made to describe AEs in terms of a diagnosis. If appropriate, component symptoms should be listed in addition to the diagnosis. If only nonspecific signs or symptoms are present, then these should be recorded as separate diagnoses in the eCRF.

All subjects who experience AEs, irrespective of whether they are considered by the investigator to be at least possibly related to treatment with the IMP, must be monitored to determine the outcome. The clinical course of each AE will be followed up according to accepted standards of medical practice, even after the subject has completed participation in the study, until a satisfactory explanation is found or the investigator considers it medically justifiable to terminate the follow-up. Should the AE result in death, a full pathologist's report should be provided, if possible.

AEs will be classified according to their severity, causal relationship to the IMPs, and seriousness.

If the AE is serious or of special interest, as defined in Section 9.3, the investigator or other authorized medical personnel at the study site must be notified and complete the paper "SAE form" at the time the SAE is detected. SAE reporting should occur within 24 h (Section 9.2.2).

### **Severity of Adverse Events**

The severity of AEs will be assessed according to the following criteria:

Mild	

• Transient or mild discomfort

• No limitation in activity

• No medical intervention or therapy required

Moderate	

• Marked limitation in activity

• Some assistance usually required

• Medical intervention or therapy required

• Hospitalization possible

Severe	

• Extreme limitation in activity

• Significant assistance required

• Significant medical intervention or therapy required

• Hospitalization or hospice care probable

### **Causal Relationship of Adverse Events**

The investigator must assess whether or not the AE is causally related to administration of the IMP. Even if the investigator considers that there is no causal relationship to the IMP, the AE must still be reported.

The causal relationship of AEs to administration of the IMP will be assessed according to the following criteria:

Not related	
 
• Event or laboratory test abnormality with a time to administration of the IMP that makes a relationship impossible
 
• Is most likely explained by concurrent disease or other drugs or chemicals (either pathophysiologically or clinically)
 
• Has occurred before administration of the IMP in comparable severity and/or frequency
 

Unlikely related	
 
• Event or laboratory test abnormality with a time to administration of the IMP that makes a relationship improbable (but not impossible)
 
• Disease or other drugs provide plausible explanations
 

Possibly related	
 
• Event or laboratory test abnormality with reasonable time relationship to administration of the IMP
 
• Could also be explained by disease or other drugs
 
• Information on IMP withdrawal may be lacking or unclear
 

Probably related	
 
• Event or laboratory test abnormality with reasonable time relationship to administration of the IMP
 
• Unlikely to be attributed to disease or other drugs
 
• Response to withdrawal clinically reasonable
 
• Rechallenge not required
 

Certainly related	
 
• Event or laboratory test abnormality with plausible time relationship to administration of the IMP
 
• Cannot be explained by disease or other drugs
 
• Response to withdrawal plausible (pharmacologically or pathologically)
 
• Event definitive pharmacologically or phenomenologically (i.e., an objective and specific medical disorder or a recognized pharmacological phenomenon)
 
• Rechallenge satisfactory, if necessary
 

All AEs classified as “possibly”, “probably”, or “certainly” related will be considered as “at least possibly related to the IMP”. All AEs classified as “not related” or “unlikely related” will be considered as “not related” to the IMP.

The degree of certainty with which an AE is attributed to administration of the IMP or an alternative cause (e.g., natural history of the underlying disease, concomitant therapy, etc.) must be determined on the basis of how well the AE can be understood in terms of:

- Known pharmacology of the IMP
- Clinically and/or pathophysiologically plausible context
- Reaction of a similar nature previously observed with similar products, or reported in the literature for similar products as being product-related (e.g., headache, facial flushing, pallor)
- Plausibility supported by the temporal relationship (e.g., the event being related by time to administration or termination of treatment with the IMP, drug withdrawal, or reproduced on rechallenge)

---

## 9.2 Serious Adverse Events

### 9.2.1 Definition of Serious Adverse Events

An AE is defined as serious (i.e., as an SAE) according to the ICH E2A guideline if any of the following criteria are fulfilled:

- Results in death
- Is life-threatening

NOTE: the term “life-threatening” in the definition of “serious” refers to an event in which the subject was at risk of death at the time of the event; it does not refer to an event which hypothetically might have caused death had it been more severe

- Requires in-patient hospitalization or prolongation of existing hospitalization
- Results in persistent or significant disability/incapacity
- Is a congenital anomaly/birth defect
- Is an important medical event that may not be immediately life-threatening or result in death or hospitalization, but may jeopardize the subject or may require intervention to prevent one of the other outcomes listed above

Medical and scientific judgement should be exercised in deciding whether expedited reporting is appropriate in other situations, such as important medical events that may not be immediately life-threatening or result in death or hospitalization but may jeopardize the subject or may require intervention to prevent one of the other outcomes listed in the definition above. These should also usually be considered serious.

The following hospitalizations are not considered to be serious AEs because there is no “adverse event” (i.e., there is no untoward medical occurrence) associated with the hospitalization:

- Hospitalization for respite care
- Hospitalization planned prior to informed consent (where the condition requiring the hospitalization has not changed after administration of IMP)

### 9.2.2 Documentation and Reporting Obligations of Serious Adverse Events

The observation period for SAEs starts with confirmation of signed informed consent at Screening (i.e., at Day -28 to Day -10) and ends at Week 44.

Any SAE judged by the investigator to be at least possibly related to treatment with the IMP should be reported to the sponsor regardless of the length of time that has passed since study completion.

SAEs have to be documented on “SAE forms” and the investigator must report them immediately to the CRO, or no later than 24 h after becoming aware of the SAE. If more information about the SAE becomes available later, this must also be reported immediately or no later than 24 h after becoming aware of the SAE.

In case of a subject’s death, the investigator will provide the applicable Ethics Committee(s) and the applicable responsible authorities with any further information requested.

In all reports, personal data are to be anonymized by using the subject identification number. It must be possible to relate the initial and all follow-up reports to each other by means of the subject identification number, or name and address, or the like.

The investigator must report all SAEs to the following address:

---

**Fax: [name]**  
**QLS\[contact]**

### **9.3 Adverse Events of Special Interest**

An AESI is an AE of scientific and medical concern specific to the sponsor's product or program, for which ongoing monitoring and rapid communication by the investigator to the sponsor could be appropriate. Such an event might require further investigation in order to characterize and understand it.

For this study, the following AEs are defined as AESIs:

- Acute systemic hypersensitivity reaction
- Meningitis
- Meningococcal septicemia
- Invasive infection

All AESIs will be recorded and reported as SAEs, and subject narratives will be generated.

### **9.4 Suspected Unexpected Serious Adverse Reactions**

#### **9.4.1 Definition of Suspected Unexpected Serious Adverse Reactions**

Suspected Unexpected Serious Adverse Reactions (SUSARs) are side effects whose nature or severity is inconsistent with the information available about the product in the Investigator's Brochure.

#### **9.4.2 Reporting of Suspected Unexpected Serious Adverse Reactions**

The sponsor will submit all available information on a SUSAR immediately to the applicable Ethics Committee, the applicable regulatory authority, and the investigators in this study, at the latest within 15 calendar days after the event becomes known.

For every SUSAR that results in death or a life-threatening condition, the responsible Ethics Committee, the applicable regulatory authority, and the investigators in this study must be informed by the sponsor within 7 calendar days after the event becomes known. Additional information has to be given within 8 further calendar days.

### **9.5 Therapeutic Procedures**

If a subject requires treatment as a result of an AE, the treatment must meet the recognized standards of medical care in order to restore the subject's health. Appropriate resuscitation devices and medication must be available in order to treat the subject as quickly as possible in the event of an emergency.

The actions taken to treat the AE/SAE must be documented by the investigator either in the appropriate eCRF and/or using additional documents.

---

## 9.6 Pregnancy

Pregnancy, by definition, is not considered as an AE unless it results in a complication (such as a maternal complication during pregnancy) that meets the definition of an AE, results in spontaneous abortion or stillbirth, or is associated with a congenital anomaly or birth defect in the fetus. Any such complication must then be reported accordingly as an SAE.

A female subject who becomes pregnant while participating in the study, or up to and including 28 days after the last dose of IMP, must notify the investigator immediately and, if appropriate, discontinue treatment with the IMP. The subject may continue other study procedures at the discretion of the investigator.

The sponsor must be notified within 5 days of the investigator becoming aware of the pregnancy, using the following address.

Fax: [name] [contact]

---

Whenever possible, a pregnancy in subjects exposed to IMP should be followed to term so as to assess any potential occurrence of congenital anomalies or birth defects. Any follow-up information, including premature termination and the status of the mother and child after delivery, should be reported by the investigator.

In certain situations, it may be necessary to monitor the development of the child for an appropriate period after birth. If this is the case, details should be included in this section.

Severe side effects and complications during a pregnancy as well as congenital birth defects are SAEs per definition and, therefore, have to be reported additionally as SAEs according to the reporting procedures described above.

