## 5.6 Procedures in Case of Specific Side Effects

To date, IFX-1 has been tested in healthy subjects and subjects with early septic organ dysfunction, complex cardiac surgery, and HS. An overview of side effects (i.e., ADRs that occurred in these studies) is provided in the Investigator's Brochure.

If a side effect occurs or is suspected after administration of IMP, subjects must be closely monitored and carefully observed, and as applicable the side effect must be reported as an AE (Section 9). Any treatment deemed as medically appropriate should be initiated.

In case of the following specific types of side effects, the procedures reported below must be applied.

**Infections:** because IFX-1 blocks C5a, there is a theoretical risk of an increased rate of infections. Therefore, the investigator (and other health care professionals who take care of the subjects) should be alert to signs and symptoms of infections in general. In case a subject develops a clinical picture that is difficult to distinguish from that associated with invasive infection, routine blood cultures and early start of antibiotic treatment is recommended. In subjects with bacterial infection, depending on the severity of the infections, it is important that concomitant antibiotic therapy be administered during treatment with IFX-1 to ensure appropriate control of the source of the infection. The investigator should pay close attention to the choice of an appropriate broad spectrum antibiotic treatment according to applicable guidelines. The IMP can be temporarily or permanently interrupted at the investigator's discretion. Any invasive infection has to be reported as an adverse event of special interest (AESI) (Section 9.3).

**Meningitis/Meningococcal Sepsis:** in case of signs of meningitis at any time during the study period, the subject must be carefully observed and the guideline for "ambulatory acquired bacterial meningoenzephalitis"[22] should be followed. This includes lumbar puncture, blood culture testing, immediate start of treatment with dexamethasone and iv antibiotics (combination therapy with ampicillin and 3rd generation cephalosporin), and search for infectious focus (e.g., computed tomography or magnetic resonance tomography). The IMP should be interrupted immediately in case of signs and symptoms of meningitis and withdrawn if meningitis is confirmed.

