### **6.2.2 Discontinuation of Treatment With Investigational Medicinal Product**

Subjects must be discontinued from treatment with the IMP under any of the following circumstances:

- Unacceptable toxicity or TEAE, as determined by the investigator
- Anaphylactic or other serious allergic reaction
- Serious infection, including meningitis and sepsis
- If, in the investigator's opinion, continued administration of IMP could be detrimental to the subject's well-being
- Use of prohibited treatment that in the opinion of the investigator or sponsor necessitates the subject being removed
- Application of lesion interventions exceeding the permitted number (see section [5.8.2.4](#))
- Biopsy confirmation of any malignancy
- Pregnancy
- Subjects who receive 800mg q4w and have a loss of response (see [Definition of Terms](#)) during the Extension Period will have an optional visit 2 weeks later. Subjects who still have a loss of response at the subsequent (planned) visit will be discontinued from the study and will not switch to the non-responder schedule
- Subjects who receive 800mg q2w and experience WOI (see [Definition of Terms](#)) at 2 consecutive visits in the Maintenance Period of the Extension Period will be discontinued from the study

Subjects who have been discontinued will have a Post-Treatment FUV 3 months after discontinuation or when another HS therapy has been started.

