### **8.3.2.6 Pregnancy Testing**

Pregnancy testing will be conducted in all women of childbearing potential.

A serum pregnancy test will be performed at Screening, at Week 44 or an early discontinuation visit and the 3-month Post-Treatment Follow-Up visit if the subject discontinues before Week 44.

An urine pregnancy test will be performed at Weeks 0 (Day 1) and 16.

For France: an urine pregnancy test will be performed in addition at Weeks 4, 8, 12, 20, 24, 28, 32, 36, 40).

If any pregnancy test is positive, the subject will not be eligible for participation or continuation in the study.

Lactating women will not be eligible for participation or continuation in the study.

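### Pregnancy has conflicting rules for stopping IMP and for staying in the study, and the infection text is not tied to the mandatory stop for serious infection

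*Combined protocol and SAP*

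**What the plan says.** **Pregnancy.** Section 6.2.2 opens its list with "Subjects must be discontinued from treatment with the IMP under any of the following circumstances", and pregnancy is one of the items, without a qualifier. Section 8.3.2.6 states: "If any pregnancy test is positive, the subject will not be eligible for participation or continuation in the study". Section 9.6 covers a subject who becomes pregnant during the study or within 28 days after her last dose. It says she "must notify the investigator immediately and, if appropriate, discontinue treatment with the IMP", and continues: "The subject may continue other study procedures at the discretion of the investigator".

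**Infection.** The list in Section 6.2.2 also contains "Serious infection, including meningitis and sepsis". The infection paragraph of Section 5.6 covers infections in general, a clinical picture hard to tell from invasive infection, and bacterial infection. For bacterial infection, subject to its severity, it says "it is important that concomitant antibiotic therapy be administered during treatment with IFX-1". It then says "The IMP can be temporarily or permanently interrupted at the investigator's discretion", and it closes by making every invasive infection an AESI. Section 5.6 presents its procedures as compulsory, and Section 1.4.2 refers sites to it for handling infections. Meningitis has a separate paragraph in Section 5.6: interrupt on signs, withdraw on confirmation.

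**The concern.** These are safety rules, so a site should find the same answer wherever it looks. For pregnancy it does not: one section removes all choice about IMP, another ends participation, and a third makes the IMP stop conditional and allows procedures to continue. For infection, the section to which sites are directed uses discretionary wording, while the mandatory stop sits elsewhere and is not mentioned there. I found no statement of which section prevails.

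At stake first is uniform handling of subjects. A secondary matter is that the same event could lead to discontinuation at one site and not at another. That changes who contributes an observed Week 16 result and, for infection, who is counted with a TEAE leading to discontinuation.

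**Working it through.** The plan gives no figure on this point, so there is nothing to reproduce. The check is a comparison of the current text.

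**1. Pregnancy**

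| Question | Section 6.2.2 | Section 8.3.2.6 | Section 9.6 |
|---|---|---|---|
| IMP | Mandatory stop | Stop implied, since the subject leaves the study | Stop is conditional |
| Study continuation | Not settled for pregnancy; gives a post-treatment visit for discontinued subjects | Ended after a positive test | Other procedures at the investigator's discretion |

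On IMP, two sections are mandatory and one is conditional. On study continuation, one section ends it, one permits procedures, and one does not settle it.

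**2. Which pregnancy text a site would use.** Outside France, the scheduled tests are at Screening, Day 1, Week 16 and Week 44 (Section 8.3.2.6; earlier if the subject discontinues). Dosing runs to Week 40 (Table 3). That leaves 44 − 16 = 28 weeks without a scheduled test, of which 40 − 16 = 24 lie within the dosing schedule. A pregnancy in that gap would probably surface through the subject's own report. That is the route described in Section 9.6, which has the permissive wording.

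**3. Infection**

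| Event | Section 6.2.2 | Section 5.6 |
|---|---|---|
| Confirmed meningitis | Mandatory stop | Withdraw: broadly consistent |
| Sepsis, other serious infection | Mandatory stop | Investigator's discretion, no exception stated |
| Invasive infection | Covered if it is a serious infection; the term is not defined | Within the discretionary paragraph |
| Other infection | Not listed by name | Investigator's discretion |

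The gap is therefore sepsis, serious infection other than meningitis, and invasive infection.

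**4. Consequence for the analysis.** Under Section 10.5.1, a missing Week 16 HiSCR is multiply imputed under missing at random, unless the subject discontinued for disease relapse, progressive disease or lack of efficacy. A subject who leaves before Week 16 because of pregnancy or infection is therefore imputed, while one who stays can supply an observed value. HiSCR is assessed at Week 16 before that visit's infusion (Section 10.4.1), so a pregnancy first found by the Week 16 test need not cost the value. Section 10.4.2 counts TEAEs leading to IMP discontinuation and to study discontinuation, so differing practice on infection can alter those counts.

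**5. Size.** Section 4.5 expects women and men in a 2:1 ratio, so about 175 × 2/3 ≈ 117 women. The number of childbearing potential is not given, and exclusion criterion 14 requires willingness and ability to use highly effective contraception. No expected rate of pregnancy or serious infection is stated, so the number of affected subjects cannot be computed.

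**The case against.** **Pregnancy, IMP.** The sentence in Section 9.6 also covers the 28 days after the last dose, when there may be no treatment left to stop. The qualifier can then mean no more than stopping if she is still being dosed, which agrees with Section 6.2.2. This is plausible, but it is not written.

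**Pregnancy, procedures.** Under Section 6.2, discontinued subjects still have end-of-study assessments and a post-treatment visit, and Section 9.6 wants pregnancies followed to term. Continuing other procedures could mean only that. Section 9.6 does not limit it so, and the tension with Section 8.3.2.6 remains.

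**Infection.** This objection is stronger. Section 5.6 is a permissive rule for infections in general, and permanent interruption is one of its options. A site that applies Section 6.2.2 to serious infection and Section 5.6 to the rest complies with both. Section 6.2.3 narrows the difference further, because a subject who omits more than 2 infusions in a period is discontinued from the study anyway. What stands is that Section 5.6 covers invasive infection, is where sites are sent, and neither excepts serious cases nor points to Section 6.2.2.

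**Stronger inferences.** A reader might infer that Sections 5.6 and 6.2.2 cover identical events, because Section 9.3 has every AESI, including invasive infection, recorded and reported as an SAE. The documents do not support this: Section 9.3 governs recording and reporting, and does not define serious infection for Section 6.2.2. A reader might also infer that the pregnancy conflict changes discontinuation-related TEAE counts. Section 9.6 says pregnancy is not an AE unless it leads to a listed complication, so an uncomplicated pregnancy would not normally enter them.

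**Conclusion.** This is an internal inconsistency in current text. The pregnancy conflict is clear: Section 9.6 disagrees with Section 6.2.2 on IMP as written and with Section 8.3.2.6 on study continuation, and even the mild reading of the qualifier leaves the second disagreement in place. The infection point is lesser. It is an undefined term and a missing link between a general discretionary rule and a specific mandatory one, and it does not extend to confirmed meningitis, where the two sections broadly agree.

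The weight lies in subject safety and uniform conduct. It might be tempting to conclude that the primary analysis is compromised, but the documents do not show that. Only exits before Week 16 matter there, few are expected, and any effect is probably small. That judgement assumes that pregnancies and serious infections are rare in this study, since the protocol gives no rates. The conclusion also assumes that no document outside the one reviewed, such as a site manual, sets an order of precedence.

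**What to change.** By amendment, the sponsor should:

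- Reconcile Sections 6.2.2, 8.3.2.6 and 9.6 so that pregnancy has one rule for IMP and one for study continuation. The text should say what the qualifier in Section 9.6 refers to and which procedures its discretion covers.
- Reconcile the infection paragraph of Section 5.6 with Section 6.2.2 by stating which prevails for serious or invasive infection, defining serious infection for that purpose, and adding a cross-reference in each section.

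Which clinical rule applies is for the sponsor to decide, and no view is taken here. The cost is wording changes and notification of sites. No new data collection, change in sample size or change in analysis method is needed.
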